7.1.4 Adverse Events of Special Interest

The Investigator will monitor each patient for clinical and laboratory evidence for pre-defined (per the results of the ongoing Phase 1 ANV419-001 study) Aes of special interest (AESIs) throughout the patient's participation in this study.

The Investigator will assess and record any additional information on the AESI in detail on an AE form which must be submitted within 24 hours of awareness of the event.

For this study, AESIs include the following:

- Grade 3 and Grade 4 CRS;
- Grade 3 and Grade 4 IRR;
- Grade 3 and Grade 4 capillary leak syndrome; and
- Grade 3 and Grade 4 immune effector cell-associated neurotoxicity syndrome (ICANS) as per the American Society for Transplantation and Cellular Therapy and National Comprehensive Cancer Network guidelines for ICANS.^{34,38}

During the course of the study, additional AESIs may be identified by the Sponsor.

AESIs must be recorded in the eCRF.

7.2 Serious Adverse Events

An AE or adverse reaction is considered serious if, in the view of either the Investigator or Sponsor, it results in any of the following outcomes:

- Death;
- A life-threatening AE;

Note: An AE or adverse reaction is considered "life-threatening" if, in view of either the Investigator or Sponsor, its occurrence places the patient at immediate risk of death. It does not include an event that, had it occurred in a more severe form, might have caused death.

Requires hospitalization or prolongation of existing hospitalizations;

Note: Any hospital admission with at least 1 overnight stay will be considered an inpatient hospitalization. An emergency room or urgent care visit without hospital admission will not be recorded as a SAE under this criterion, nor will hospitalization for a procedure scheduled or planned before signing of informed consent, or elective treatment of a pre-existing condition that did not worsen from Baseline Visit. However, unexpected complications and/or prolongation of hospitalization that occur during elective surgery should be recorded as Aes and assessed for seriousness. Admission to the hospital for social or situational reasons (ie, no place to stay, live too far away to come for hospital visits, respite care) will not be considered inpatient hospitalizations.

- A persistent or significant disability/incapacity or substantial disruption of the ability to conduct normal life functions:
- A congenital anomaly/birth defect; or
- An important medical event.

Note: Important medical events that do not meet any of the above criteria may be considered an SAE when, based upon appropriate medical judgment, they may jeopardize the patient and may require medical or surgical intervention to prevent one of the outcomes listed above. Examples of such medical events include allergic bronchospasm requiring intensive treatment in an emergency room or at home, blood dyscrasias or convulsions that do not result in inpatient hospitalizations, or the development of drug dependency.

Note: Events of progression of a patient's underlying cancer, as well as, events clearly related to the progression of a patient's cancer (signs/symptoms of progression) should not be reported as an SAE unless the outcome is fatal during the study or within the safety reporting period. If the event has a fatal outcome during that timeframe, the event of Progression of "Type of Cancer" must be recorded as an SAE with NCI CTCAE Grade 5 (fatal) outcome indicated. Diagnosis of progression of disease or hospitalization due to signs and symptoms of disease progression alone should not be reported as an SAE.

7.3 Serious Adverse Event Reporting – Procedures for Investigators

Initial reports

All SAEs occurring from signing of informed consent until the Safety Follow-Up Visit up to 90 days after the last dose of study drug, or the start of a new cancer regimen, whichever is shorter, must be reported to Medpace Clinical Safety within 24 hours of the knowledge of the occurrence.

After the reporting window, any SAE that the Investigator considers related to study drug must be reported to the Medpace Clinical Safety or the Sponsor/designee.

To report the SAE, complete the SAE form electronically in the electronic data capture (EDC) system for the study. When the form is completed, Medpace Safety personnel will be notified electronically by the EDC system and will retrieve the form. If the event meets serious criteria and it is not possible to access the EDC system, send an email to Medpace Safety at [contact] or call the Medpace SAE reporting line (phone number listed below), and fax/email the completed paper SAE form to Medpace (contact information listed in Section 7.6) within 24 hours of awareness. When the EDC system becomes available, the SAE information must be entered within 24 hours of the system becoming available.

Follow-up reports

The Investigator must continue to follow the patient until the SAE has subsided or until the condition becomes chronic in nature, stabilizes (in the case of persistent impairment), or the patient dies or is considered lost to follow-up.

Within 24 hours of receipt of follow-up information, the Investigator must update the SAE form electronically in the EDC system for the study and submit any supporting documentation (eg, patient discharge summary or autopsy reports) to Medpace Clinical Safety via fax or email. If it is not possible to access the EDC system, refer to the procedures outlined above for initial reporting of SAEs.

7.4 Pregnancy Reporting

If a patient becomes pregnant after the start of study drug or within6 months after the last dose of study drug, the Investigator is to stop dosing with study drug(s) immediately if applicable and the patient should be withdrawn from the study. End of Study procedures should be implemented at that time.

A pregnancy is not considered to be an AE or SAE; however, it must be reported to Medpace Clinical Safety within 24 hours of knowledge of the event. Medpace Clinical Safety will then provide the Investigator/site the Exposure In Utero (EIU) form for completion. The Investigator/site must complete the EIU form and fax/email it back to Medpace Clinical Safety.

If the female partner of a male patient becomes pregnant while the patient is receiving study drug or6 months after the last dose of study drug, the Investigator should notify Medpace Clinical Safety as described above.

The pregnancy should be followed until the outcome of the pregnancy, whenever possible, and until 8 weeks after delivery to assess for congenital defects. Once the outcome of the pregnancy is known, the EIU form should be completed and faxed/emailed to Medpace Clinical Safety. If the outcome of the pregnancy meets the criteria for immediate classification as an SAE (ie, postpartum complication, spontaneous abortion, stillbirth, neonatal death, or congenital anomaly), the Investigator should follow the procedures for reporting an SAE.

7.5 Expedited Reporting

The Sponsor/designee will report all relevant information about Suspected Unexpected Serious Adverse Reactions (SUSARs) that are fatal or life-threatening as soon as possible to the FDA, applicable competent authorities in all the Member States concerned, and to the Central Ethics Committee, and in any case no later than 7 days after knowledge by the Sponsor/designee of such

a case. Relevant follow-up information will subsequently be communicated within an additional 8 days.

All other SUSARs will be reported to the FDA, applicable competent authorities concerned and to the Central Ethics Committee concerned as soon as possible but within a maximum of 15 days of first knowledge by the Sponsor/designee.

The Sponsor/designee will also report any additional expedited safety reports required in accordance with the timelines outlined in country-specific legislation.

The Sponsor/designee will also inform all Investigators as required per local regulation.

The requirements above refer to the requirements relating to investigational medicinal product.

Expedited reporting of SUSARs related to all investigational medical products (IMPs), (ie, ANV419, pembrolizumab, and ipilimumab) is required. Expedited reporting of SUSARs, related to non-IMPs (NIMPs) is not required. Listings of cases related to NIMPs will be included in the Development Safety Update Report.

[figure not shown]
7.6 Special Situation Reports

Special situation reports include reports of overdose, misuse, abuse, medication error, and reports of adverse reactions associated with product complaints.

- Overdose: Refers to the administration of a quantity of a medicinal product given per administration or cumulatively (accidentally or intentionally), which is above the maximum recommended dose according to the Protocol. Clinical judgment should always be applied. In cases of a discrepancy in the drug accountability, overdose will be established only when it is clear that the patient has taken additional dose(s) or the Investigator has reason to suspect that the patient has taken additional dose(s).
- **Misuse:** Refers to situations where the medicinal product is intentionally and inappropriately used not in a way that is not in accordance with the Protocol instructions or local prescribing information and may be accompanied by harmful physical and/or psychological effects.
- **Abuse:** Is defined as persistent or sporadic, intentional excessive use of a medicinal product, which is accompanied by harmful physical or psychological effects.
- **Medication error:** Is any unintentional error in the prescribing, dispensing, or administration of a medicinal product by a healthcare professional, patient, or consumer, respectively. The administration or consumption of the unassigned treatment and administration of an expired product are always reportable as medication errors, cases of patients missing doses of investigational product are not considered reportable as medication error.
- **Product complaint:** Is defined as any written, electronic, or oral communication that alleges deficiencies related to the identity, quality, durability, reliability, safety, effectiveness, or performance of a drug or device after it is released for distribution. A special situations form will only be completed if a complaint is associated with an adverse drug reaction.

All special situation events as described above must be reported on the Special Situations Report form and faxed/emailed to Medpace Clinical Safety (contact information listed below) within 24 hours of knowledge of the event. All Aes associated with these Special Situation reports should be reported as Aes or SAEs as well as recorded on the AE eCRF and/or the SAE report form.

Details of the symptoms and signs, clinical management, and outcome should be provided, when available.

7.7 Clinical Laboratory Assessments

Clinical laboratory assessments (urinalysis, coagulation, chemistry, serology, endocrinology, and hematology) will be performed locally as indicated in Appendix A and will include the laboratory analytes presented in Appendix B. Patients found to have treatment-emergent laboratory toxicity of Grades 3 or 4 will be monitored at least weekly until resolution. Urinalysis may be done by dipstick or microscopy.

If applicable for logistical reason, clinical laboratory assessments can be performed within 24 hours from ANV419 administration.

7.8 Vital Signs

Vital signs will be measured as indicated in the Appendix A and will include measurements of systolic and diastolic blood pressure, heart rate, respiratory rate, and body temperature.

7.9 Electrocardiograms

Electrocardiograms will be performed as indicated in Appendix A. Twelve-lead ECGs will be performed locally and should be collected in triplicate, separated by approximately 5 minutes. When ECG measurements coincide with blood sample draws for PK, PD, or ADA sampling, the ECG measurement should be timed sufficiently prior to blood sample collection without impacting the sample collection time. Additional triplicate ECGs may be performed as clinically indicated. The patient should be relaxed and in a recumbent or semi-recumbent position at least 5 minutes before recording an ECG. ECGs will be reviewed locally by the site and parameters will be entered into the EDC.

7.10 Physical Examinations

Physical examinations will be performed as indicated in Appendix A.

A full physical examination and review of relevant systems, including height, will occur at the Height will be measured at baseline only. Symptom-directed physical examination measurements are to be performed at all other visits and as clinically indicated.

8 STATISTICS

A Statistical Analysis Plan (SAP) will be prepared as a separate document. The SAP will include a more technical and detailed description of the planned statistical summaries and will be finalized prior to any interim analysis.

8.1 Analysis Populations

The Safety Population will consist of all patients who receive at least 1 dose (or partial dose) of study drug(s). The Safety Population will be used for safety analyses including DLT assessments.

The Efficacy Population will consist of all patients who receive at least 1 dose of study drug, have at least 1 post-baseline tumor assessment, and who are part of the Monotherapy Dose Expansion part, Combination Dose Finding part, or the Combination Dose Expansion part. The Efficacy Population will be used for efficacy analyses.

The PK Population will consist of all patients who receive at least 1 dose of study drug and have at least 1 measured concentration for at least 1 of the analytes. The PK Population will be used for PK analyses.

The PD Population will consist of all patients who receive at least 1 dose of study drug and have at least 1 evaluable pharmacodynamic sample. The PD Population will be used for PD endpoint analyses.

8.2 Statistical Methods

8.2.1 Sample Size Determination

Monotherapy Dose Expansion part

This part of the study will use Bayesian sequential monitoring. A maximum of 15 patients will be enrolled and treated at each dose level arm. Aland A2 monotherapy arms will be analyzed as independent experiments, and also overall, and the following assumptions are made:

- Nothing is known *a priori*: assume a uniform prior, ie, the true ORR could be any value between 0% and 100%;
- A true ORR <6% indicates treatment failure; and
- A true ORR >10% indicates treatment success.

With a maximum of 15 patients in an arm, if no responses were observed, then the estimated true ORR would be 5.9%, with 90% confidence interval (CI) (0.3%, 17.1%). This would be sufficient evidence to suggest that the treatment is unlikely to be successful. With a maximum of 30 patients overall, if no responses were observed, then the estimated true ORR would be 3.1%, with 90% CI (0.2%, 9.2%). This would be sufficient evidence to suggest that the treatment at either dose is unlikely to be successful.

There is 95% certainty that the true ORR is greater than 10% if any 1 of the following are observed:

- 2 responses in 3 to 7 patients;
- 3 responses in 8 to 13 patients;
- 4 responses in 14 to 19 patients; or

• 5 responses in 20 to 27 patients.

Combination Dose Finding part

The Combination Dose Finding part will employ BOIN²⁹ to find the MTD/RP2D of Arm B (ANV419 in combination with pembrolizumab) and Arm C (ANV419 in combination with ipilimumab). For each arm, the following assumptions have been predefined for the dose escalation:

- Target DLT rate of 25%;
- Maximum of 25 patients;
- Maximum of 9 patients treated at the same dose level; and
- Maximum of 5 dose levels defined in Table 5 to be tested.

Patients will be enrolled and treated in cohorts of 3 patients (at least). Up to 50 patients in total will be enrolled for the Combination Dose Finding part, with a minimum of 6 patients treated at RP2D.

Combination Dose Expansion part (efficacy analysis)

The sample size calculation is based on a Simon's 2-stage⁴⁰ design and ensures that under all possible distributions of patients to the 2 treatment arms, there is at least 80% power to correctly detect an ORR >40% and at most a Type I error rate of 10% of rejecting a null hypothesis that ORR <20%. This results in a sample size of 12 patients randomized to each treatment arm in Stage 1, followed by 13 additional patients randomized during Stage 2: a total of 25 patients per arm at the end of Stage 2.

8.2.2 Baseline Characteristics

Demographics (ie, date of birth, race, ethnicity, and sex of the patient as allowed per local guidelines), and patients' baseline clinical characteristics will be summarized for each arm by dose level in the Combination Dose Finding part of the study and by treatment arm in the Monotherapy Dose Expansion part and Combination Dose Expansion part and overall using descriptive statistics.

8.2.3 Interim Efficacy Analysis

In Arm B or C, an interim analysis of the primary outcome will be performed at the end of Stage 1 of the Combination Dose Expansion part of the study (once 12 evaluable patients have completed at least 1 disease evaluation or have discontinued from the study). Any treatment arm with an ORR <20% per RECIST (ie, treatment arms with no more than 2 complete or partial responses) will be discontinued.

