Evaluation of n	on-target lesions							
	Disappearance of all nontarget lesions and							
Complete response	normalization of tumor marker level.							
	Persistence of 1 or more nontarget lesion(s) and/or							
	maintenance of tumor marker level above the normal							
Incomplete response/Stable disease	limits.							
	Appearance of 1 or more new lesions and/or							
Progressive disease	unequivocal progression of existing nontarget lesions.							
LD = longest diameter; PR = partial response; SAD = short axi								
Source: Eisenhauer EA, Therasse P, Bogaerts J, et al. Ne	ew response evaluation criteria in solid tumours: revised							
RECIST guideline (version 1.1). Eur J Cancer. 2009;450								

APPENDIX D: MODIFIED RESPONSE EVALUATION CRITERIA IN SOLID TUMORS 1.1 FOR IMMUNE-BASED THERAPEUTICS (IRECIST) QUICK REFERENCE

The principles used to establish objective tumor response are largely unchanged from Response Evaluation Criteria in Solid Tumors (RECIST) 1.1, but the major change for immune-RECIST (iRECIST) (ie, Modified Response Evaluation Criteria in Solid Tumors 1.1 for immune-based therapeutics) is the concept of resetting the bar if RECIST 1.1 progression is followed at the next assessment by tumor shrinkage. iRECIST define immune-unconfirmed progressive disease (iUPD) on the basis of RECIST 1.1 principles; however, iUPD requires confirmation, which is done on the basis of observing either a further increase in size (or in the number of new lesions) in the lesion category in which progression was first identified in (ie, target or nontarget disease), or progression (defined by RECIST 1.1) in lesion categories that had not previously met RECIST 1.1 progression criteria. However, if progression is not confirmed but instead tumor shrinkage occurs (compared with baseline), which meets the criteria of immune-complete response, immune-partial response, or immune-stable disease, then the bar is reset so that iUPD needs to occur again (compared with nadir values) and then be confirmed (by further growth) at the next assessment for immune-confirmed progressive disease to be assigned. If no change in tumor size or extent from iUPD occurs, then the time point response would again be iUPD. This approach allows atypical responses, such as delayed responses that occur after pseudo-progression, to be identified, further understood, and better characterized.

See Table 23 for a comparison between RECIST 1.1 and iRECIST.

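### The Part 3 futility stop (2 or fewer responses in 12) may be taken after a single disease evaluation per patient, so stable disease that later becomes a response counts against an active arm

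*Protocol*

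**What the plan says.** Protocol 8.2.1 states: "The sample size calculation is based on a Simon's 2-stage" design, with a null ORR of 20%, a type I error of at most 10%, and at least 80% power at an ORR above 40%. It gives "12 patients randomized to each treatment arm in Stage 1" and "a total of 25 patients per arm at the end of Stage 2". SAP 2.2.4 repeats this. Neither document gives the final Simon boundary.

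Protocol 3.1.3 (Table 8) discontinues an arm with 2 or fewer responses among the 12 and continues it with at least 3. Protocol 8.2.3 sets the timing: the analysis is done "once 12 evaluable patients have completed at least 1 disease evaluation or have discontinued from the study". SAP 4 uses the same words. Neither asks for a second scan, a minimum follow-up, or a wait for patients still in stable disease.

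The endpoint looks further ahead. Protocol 8.2.4 and SAP 3.4.2.1 define ORR by best overall response, and Protocol Appendix C takes that over the whole sequence of recorded statuses.

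The documents differ on how binding the stop is. Protocol 8.2.3 and SAP 4 make it mandatory. The notes to the study design figures (Protocol Synopsis, Protocol 3.1, SAP 2.2.1) make it permissive.

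**The concern.** Simon's calculation treats each Stage 1 patient's response status as final when the 2-of-12 rule is applied. The timing rule does not secure that. A patient with stable disease at scan 1 who converts to PR or CR at scan 2 or later is a true responder for the final analysis but is missed at an interim taken after one scan. Missed responses can only push the Stage 1 count down. The error therefore runs one way: active arms are stopped too often, and the type I error falls rather than rises. At stake is a combination arm dropped because its data are immature, under a sample-size section that promises at least 80% power and makes no allowance for late response.

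**Working it through.** **Inputs from the documents.** p0 = 0.20, p1 = 0.40, alpha at most 0.10, power at least 0.80, n1 = 12, n = 25 (Protocol 8.2.1); stop if 2 or fewer of 12 (Protocol 3.1.3 and 8.2.3).

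**Assumption.** f is the share of true responses first visible after scan 1. The documents give no value, so a range is shown.

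**Step 1: reproduce the design.** With X ~ Bin(12, p) and Y ~ Bin(13, p), P(declare active) = Σ over x ≥ 3 of P(X = x) · P(Y ≥ r + 1 − x). A search over all two-stage designs meeting the stated limits returns 2/12, 7/25 as Simon's optimal design, with success at 8 or more of 25. It gives alpha 9.9% and power 81.5%, so the stated design is reproduced. The spare power is 81.5 − 80 = 1.5 points.

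**Step 2: false stop with complete information.** At ORR 40%, P(X ≤ 2) = 0.6^12 + 12(0.4)(0.6^11) + 66(0.16)(0.6^10) = 0.0022 + 0.0174 + 0.0639 = 0.083.

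**Step 3: one scan per patient.** Each true responder is visible at the interim with probability 1 − f, so the visible count V ~ Bin(12, p(1 − f)). False stop = P(V ≤ 2). Power = Σ P(X = x) · P(V ≥ 3 | X = x) · P(Y ≥ 8 − x), with all true responses counted at the final analysis. For f = 0.20, p(1 − f) = 0.32 and P(V ≤ 2) = 0.0098 + 0.0552 + 0.1429 = 0.208.

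Results when all 12 patients have had exactly one scan:

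| Late share f | False stop at ORR 40% | Power at ORR 40% | Type I error |
|---|---|---|---|
| 0% | 8.3% | 81.5% | 9.9% |
| 5% | 10.7% | 79.9% | 9.5% |
| 10% | 13.5% | 77.9% | 9.1% |
| 20% | 20.8% | 72.2% | 8.0% |
| 30% | 30.4% | 64.3% | 6.7% |

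**Step 4: staggered accrual.** The rule asks for at least one evaluation, so earlier patients may have had more. Suppose half are already fully assessed and f = 20% applies to the rest. The average visible probability is (0.40 + 0.32)/2 = 0.36, the same as f = 10% in everyone: false stop 13.5%, power 77.9%. Treating exactly six patients as fully assessed gives 13.4% and 78.0%.

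**Step 5: the written final criterion.** Protocol 8.2.4 asks for a 95% CI lower limit above 20%. By Clopper-Pearson (SAP 3.4.3), 9/25 gives 18.0% and 10/25 gives 21.1%, so at least 10 of 25 are needed. With the same Stage 1 rule, power at ORR 40% is then 56.9% at f = 0 and 52.5% at f = 20%.

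**The case against.** Four points on the other side carry weight.

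First, a reader might infer that 80% power is lost once about 5% of responses are late. The crossing does fall there (4.8%), but only if all 12 patients have exactly one scan, and the shortfall at 5% is 0.1 point. It comes early because the design has just 1.5 points to spare. If half the patients are fully assessed, the crossing moves to about 10%. A material loss needs a late share of about 20% or more, which the documents neither support nor refute.

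Second, a reader might infer from Appendix D, which mentions "delayed responses that occur after pseudo-progression", that the protocol itself predicts the responses at issue. It does not. That sentence concerns iRECIST, while the interim and the primary endpoint use RECIST 1.1. Table 23 in the same appendix says RECIST does not allow a response after progression criteria have been met. Such responses never enter the primary ORR, so missing them costs no power. The relevant group is stable disease converting to PR or CR, for which the documents give no rate.

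Third, the 80% rests on a boundary the text does not state. Under the criterion in Protocol 8.2.4, power is 56.9% with no late responses at all. That is a separate and larger gap.

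Fourth, the figure notes make the stop permissive, and SAP 4 provides for ongoing review of efficacy data by the Safety Review Committee, so a mechanical stop is not certain. The operative rule in both documents is nevertheless mandatory.

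These points limit the size of the problem. None supplies the missing follow-up requirement.

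**Conclusion.** The concern holds as a conditional weakness in the timing rule. Protocol 8.2.3 and SAP 4 permit a mandatory futility stop on one scan per patient for an endpoint defined over all scans. In the worst case the rule permits, the chance of wrongly stopping an arm with ORR 40% rises from 8.3% to 13.5%, 20.8% or 30.4% at late shares of 10%, 20% or 30%. Power falls from 81.5% to 77.9%, 72.2% or 64.3%. With half the patients fully assessed, a 20% late share costs about as much as 10% in everyone.

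These figures rest on the derived boundary of 2/12, 7/25, on an assumed late share, and on a stop applied as written. The scan interval is redacted, so how mature a first scan would be cannot be judged. It would go too far to say that the timing rule alone removes the 80% power, or that correcting it would deliver 80% under the final criterion as written.

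SAP 1 and SAP 5 record that the trial ended after Part 1 and that no Part 3 analysis will be done. No reported result is affected; the point matters if this design is used again.

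**What to change.** In Protocol 8.2.3 and SAP 4, in identical words:

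- An arm continues as soon as 3 responses have been seen among its 12 Stage 1 patients.
- The stop for 2 or fewer responses is applied only when each of the 12 has had at least two post-baseline disease evaluations, or has earlier progressed, died or discontinued.
- The stop is described as either mandatory or permissive throughout, so that the figure notes agree with the operative text.

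Sample size and boundaries do not change, and the type I error stays at or below 9.9%. If two evaluations capture all responses, power under the derived boundary returns to 81.5% and the false stop to 8.3%. If some responses come later still, the table applies with that smaller share.

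The cost is a wording change plus up to about one scan interval of delay before a low-response arm is stopped. The mismatch between the Simon boundary and the final criterion in Protocol 8.2.4 needs its own correction.
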